### 13.1.3. Infusion-associated Reactions

An IAR is defined as a disorder characterized by 1 or more adverse reaction(s) to the infusion of pharmacological or biological substances. These reactions are classified into 2 major subtypes, early and late, according to the time interval between the infusion and the onset of an infusion-related AE.

The reactions are divided into 5 severity grades as follows:

1. Mild (requires observation only); for example, transient flushing or rash
2. Moderate (minimal, usually oral, intervention suffices); for example, urticaria/myalgia/drug fever
3. Severe (vital organ involved yet not in a life-threatening manner; usually requires parenteral medication); for example, bronchospasm/angioedema/hypotension
4. Life threatening (multisystem involvement of vital organs, urgent and critical care required); for example, systemic anaphylactic reaction
5. Death

Early IARs is any symptom or sign occurring during or within 24 hours of completion of the infusion and deemed a drug-related AE by the investigator, unless an alternative obvious explanation exists, eg, mechanical fall. Early IARs commonly involve 1 or more of the following systems: skin (urticaria and erythema), eyes (conjunctivitis), nasopharynx (rhinorrhea, rhinitis), bronchopulmonary tissues (wheezing, bronchospasm), and gastrointestinal tract (diarrhea, vomiting).

Late IAR is any symptom or sign occurring more than 24 hours (usually 1 to 3 days) after completion of the infusion that, in the investigator's opinion, fits the clinical description of a symptom or sign associated with an IAR. The most common symptoms of late IARs are pruritic skin eruptions, fever, malaise, and polyarthralgia.

Note: The list of IAR symptoms provided in [Table 9](#) is not comprehensive. It is meant to serve as a guideline to the investigators to report and manage IAR as AE. [Table 9](#) also provides a guideline for management of IARs and anaphylaxis (see also [Appendix 2](#)). The guideline is intended for sites that do not have such procedures in place. It is at the investigator's discretion to follow the guidelines or implement treatment protocol that their center is accustomed to following.

When an IAR occurs, it is important to report and indicate in the eCRF all AEs that are associated with the IAR. All available details of the events observed with an IAR are necessary to assess the evolution of the AEs after premedication for subsequent infusions.

In the event that a subject experiences an IAR, the subject should be premedicated for subsequent infusions with antihistamines, steroids, and/or acetaminophen, infusion rate adjustments, or other steps taken. If these measures are not successful, the investigator/designee should contact the medical monitor for guidance. The premedications should be continued for all remaining infusions.

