#### 5.2.2. Baseline Characteristics

- Continuous: 6MWD; FVC (sitting % predicted); CK; Hex4; age at first dose of prior ERT treatment (years) before entering Study ATB200-03 (for subjects who are ERT-experienced as defined in Section 4.3.1); and the duration of the prior ERT treatment (for subjects who are ERT-experienced as defined in Section 4.3.1)
- Categorical:
  - Age at first dose of prior ERT treatment (years) categorized:  
< 18 years, ≥ 18 to < 35 years, ≥ 35 to < 50 years, ≥ 50 years
  - Subjects with history of falls (Y, N) at the baseline in Study ATB200-07;

- Subjects with history of IARs (Y, N) at the baseline in Study ATB200-07;
- Prior pre-infusion medications versus no prior pre-infusion medications at the baseline in Study ATB200-07.

For partial dates involving age at diagnosis and age at first dose of prior ERT treatment, missing day will be imputed as ‘01,’ and missing month will be imputed as ‘JANUARY.’

The demographic and baseline characteristics summary will also be presented by the prior ERT status (ERT-experienced versus previously ERT-naïve).

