### **5.2.4. Prior and Concomitant Medications and Nondrug Therapies**

Prior medications/nondrug therapies are defined as any medication or nondrug therapy that a subject receives prior to the start of the study drug. Concomitant medications/nondrug therapies are defined as those that (a) a subject receives prior to first dose of study drug and continues after the first dose of study drug, or (b) those medications and nondrug therapies that are initiated after the first dose of study drug. Medications/nondrug therapies that are initiated after the last dose of study drug will not be considered as concomitant medications.

Prior and concomitant medications will be coded using the World Health Organization Drug Dictionary (Global B3, March 2020). The number and percentage of subjects receiving prior medication, and number and percentage of subjects receiving concomitant medication will be summarized by anatomical therapeutic chemical (ATC) class of level 4 and preferred drug name for the OLE safety population and presented by treatment group. The summary results will be presented in order of decreasing frequency of the most common medication administered to the overall treatment group.

In addition to the summary of prior and concomitant medications, the pre-infusion medications will also be summarized. Both prior pre-infusion medication (ie, pre-infusion medications taken before the first dose of cipaglucosidase alfa IV infusion study drug) and pre-infusion medications during the study (ie, those that start on or after the first dose of study drug but before the last dose of study drug) will be summarized by treatment group and overall, for the OLE safety population.

A listing of all pre-infusion medications will be provided, and this display will include columns for subject ID, prior ERT status, ATC Level 4/drug name/report name, start date and time relative to Day 1, end date and time relative to Day 1, dose (unit)/route/frequency, ‘taken before start date?’, and ‘taken during start date?.’

Separate listings will be provided for all prior and concomitant medications, and all prior and concomitant nondrug therapies.

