### **7.2.2.4. Analysis of Subjects with IARs and Time to First IAR-TEAE**

For subjects with IAR-TEAEs, a summary table will be provided displaying the following:

- Summary of IAR-TEAEs by subjects with IARs:
  - the number and percentage of subjects with IAR-TEAEs
  - total number of IAR-TEAEs
  - the number of subjects who experienced 1, 2, 3, 4 to 6, 7 to 10, 11 to 19, and  $\geq 20$  IARs in each treatment group and overall
- Time to first IAR-TEAE for subjects with IARs:
  - the time (in weeks) from the first dose of study drug to the onset of the first TEAE that is an IAR (ie, IAR-TEAE) will be calculated for each subject as:  
$$\text{Time to first IAR-TEAE (Weeks)} = (\text{date of the first IAR-TEAE} - \text{date of first dose of study drug in ATB200-07} + 1) / 7.$$
  - The calculated times will be summarized as a continuous variable and included in the same table.

In addition, a listing displaying the number of infusions and infusions that were associated with IARs by each individual subject who had an IAR will be provided. For each subject, this listing

includes subject ID, whether or not pre-infusion medication was given, number of infusions received, number of infusions that were associated with IARs, percentage of infusions associated with IARs, a chronological listing of the number of IARs corresponding to (or associated with) each infusion, and time to first IAR.

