#### **7.2.2.5. Analysis of IARs by Onset Intervals**

The IARs will also be analyzed by onset intervals categorized as follows:

- 1 to 3 days, 4 to 7 days, 8 to 14 days, 15 to 28 days, 29 days to  $\leq$  3 months, > 3 months to  $\leq$  6 months, > 6 months to  $\leq$  12 months, > 12 months to  $\leq$  2 years, > 2 years to  $\leq$  3 years, > 3 years to  $\leq$  4 years, and > 4 years.

The event rates and changes in severity over time (over these intervals) will be summarized for each treatment group. This analysis will further describe the clinical characteristics of IARs and help determine whether the IARs disappear over time or appear late.

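### SAP 7.2.2.5 tabulates IARs over time without regard to the premedication and rate changes that each IAR triggers, so a fall across intervals cannot show that IARs disappear

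*Protocol*

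**What the plan says.** Protocol 13.1.3 states that after an IAR "the subject should be premedicated for subsequent infusions with antihistamines, steroids, and/or acetaminophen, infusion rate adjustments, or other steps taken". On duration it says: "The premedications should be continued for all remaining infusions". The wording is advisory (should, not must) and is not limited to severe reactions. The same section says that full details of each IAR are "necessary to assess the evolution of the AEs after premedication for subsequent infusions".

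SAP 7.2.2.5 divides IAR onset into intervals running from the first days to beyond 4 years. It states: "The event rates and changes in severity over time (over these intervals) will be summarized for each treatment group". The stated purpose is to "help determine whether the IARs disappear over time or appear late". That section does not mention premedication or infusion rate.

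Premedication appears elsewhere in the SAP:

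- Section 5.2.2 tabulates a baseline characteristic: "Prior pre-infusion medications versus no prior pre-infusion medications at the baseline in Study ATB200-07".
- Section 5.2.4 says: "In addition to the summary of prior and concomitant medications, the pre-infusion medications will also be summarized". It also plans a listing with start and end times relative to Day 1.
- Section 7.2.2.4 plans a listing for each subject with an IAR that shows "whether or not pre-infusion medication was given, number of infusions received, number of infusions that were associated with IARs", with a chronological count of IARs per infusion.

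Section 6.3 plans IAR summaries by prior ERT status. No summary crosses IAR rate or severity over time with premedication or infusion rate.

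**The concern.** Under the protocol's rule, a subject's first IAR changes how later infusions are given. The share of infusions under such management should therefore rise with time, and rise most among those likeliest to react. An IAR rate that falls across the intervals is what fading reactivity would produce. It is also what constant reactivity under growing suppression would produce. Stating the denominator or the start of the clock more precisely would not separate the two, because the co-treatment itself changes over time.

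Long-term safety and tolerability is the primary objective, and 7.2.2.5 is the analysis the SAP assigns to the question whether IARs persist. If a fall were read as IARs disappearing, the report could understate the reaction risk that remains without that management.

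**Working it through.** The documents state no figure on this point, so there is nothing to reproduce. What follows illustrates how large an apparent fall could arise with no true change in risk.

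**Inputs from the documents.** Infusions are every 2 weeks, so 26 a year (Protocol 8.1). About 110 subjects are planned (Protocol 9.1). Management lasts for all later infusions once triggered (Protocol 13.1.3).

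**Assumed inputs.** The mean IAR risk per infusion, m, is 0.8% or 2%. Subject risks follow a gamma distribution with shape 0.5. After the first IAR the risk is multiplied by a ratio r of 0.7, 0.5 or 0.3. The documents give none of these values.

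**Formula.** A subject with constant risk p has had no IAR before infusion k with probability (1 − p)^(k−1). The expected rate at infusion k is then E{p[1 − (1 − r)(1 − (1 − p)^(k−1))]}. Let S be the average over a year of E[p(1 − p)^(k−1)]/m, that is, the share of total underlying risk held by subjects who have not yet reacted. The yearly rate is m[1 − (1 − r)(1 − S)].

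S is 0.773 in year 1 (infusions 1 to 26) and 0.261 in year 4 (infusions 79 to 104) at m = 0.8%. At m = 2% it is 0.581 and 0.100.

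Worked case, m = 0.8% and r = 0.5: year 1 is 0.8 × (1 − 0.5 × 0.227) = 0.709%; year 4 is 0.8 × (1 − 0.5 × 0.739) = 0.504%; the fall is 1 − 0.504/0.709 = 28.9%.

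| m | r | Year 1 | Year 4 | Apparent fall |
|---|---|---|---|---|
| 0.8% | 1.0 | 0.800% | 0.800% | 0% |
| 0.8% | 0.7 | 0.745% | 0.622% | 16.5% |
| 0.8% | 0.5 | 0.709% | 0.504% | 28.9% |
| 0.8% | 0.3 | 0.673% | 0.386% | 42.6% |
| 2% | 0.7 | 1.749% | 1.460% | 16.5% |
| 2% | 0.5 | 1.582% | 1.100% | 30.4% |
| 2% | 0.3 | 1.414% | 0.740% | 47.7% |

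Simulations of 110 subjects and 104 infusions agree, at about 17% to 49%. By year 4 about 36% (m = 0.8%) or 54% (m = 2%) of infusions are premedicated. With no premedication effect the rate is flat.

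**Subjects already premedicated at entry.** The table starts everyone unpremedicated, which is an upper-side case. Assume instead that 30% are premedicated at entry and that half of subjects have had 26 earlier infusions under the same rule. At m = 0.8%, simulation gives falls of about 8%, 19% and 32%. The formula, with entry premedication unrelated to risk, gives nearly the same. S among the other 70% averages 0.63 in year 1 and 0.23 in year 4, so at r = 0.5 the rates are 0.8 × [0.3 × 0.5 + 0.7 × (1 − 0.5 × 0.37)] = 0.576% and 0.8 × [0.15 + 0.7 × (1 − 0.5 × 0.77)] = 0.464%, a fall of 19%.

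**Chance variation.** In the 0.8% setting with everyone starting unpremedicated, expected yearly counts move only from about 21 to 18 (r = 0.7) or 20 to 14 (r = 0.5). Year 4 equals or exceeds year 1 in 32% or 17% of simulated trials.

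**Two tempting splits.** Splitting by premedication status at each infusion creates its own artefact. With no premedication effect at m = 0.8%, the unpremedicated stratum falls from 0.68% to 0.32% and the premedicated stratum from 2.14% to 1.64%, by selection alone, because reactors move between strata. Relying on the group premedicated at baseline also fails. If a further IAR triggers extra steps with assumed risk ratios of 0.7, 0.5 or 0.3, that group falls by roughly 15% to 34% with no true fading. It also yields only about 3 to 5 IARs a year.

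**The case against.** The strongest reply has four parts.

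First, a reader might infer that the SAP will report a premedication effect as IARs fading. The documents do not support that. The SAP says only that the table will help determine the matter, pre-specifies no conclusion and plans no formal safety tests. A subject's first IAR also precedes the management that it triggers, so this mechanism does not distort first IARs that appear late, which is the other half of the stated purpose.

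Second, the listing in 7.2.2.4 and the summaries and dated listing in 5.2.4 would let a careful author qualify a trend. That is true, but they are raw material. Nothing in the plan requires the two to be put together, although Protocol 13.1.3 itself gives the course of events after premedication as a reason for collecting the details.

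Third, IAR frequency under protocol management is a legitimate description for a long-term tolerability objective. This stands, and the fix keeps it: the table remains and is labelled as what it is.

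Fourth, the size is assumed and could be small. This also stands. The direction has support in the protocol, since Section 6.6 describes IARs as manageable with measures that include premedication and slowing or pausing the infusion. The amount has none. Because the protocol wording is advisory and allows rate changes or other steps, premedication status alone will not capture all of the management.

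**Conclusion.** The point holds in a limited form. The 7.2.2.5 table cannot separate falling reactivity from reactions suppressed by premedication or rate changes, so it cannot by itself show whether IARs disappear. With constant underlying risk the apparent fall from year 1 to year 4 is about 17% to 49% if all start unpremedicated, and about 8% to 32% at 0.8% mean risk under the assumed entry premedication and run-in. These figures rest on the assumed risk, its spread between subjects and the assumed effect of management. They show that the problem can be material, not how large it will be.

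A reader might also infer that subjects premedicated at the ATB200-07 baseline give a clean answer. They do not. SAP 5.2.4 defines prior pre-infusion medication as taken before the first infusion, which does not establish that it continued, and later IARs can still lead to rate changes or other steps in that group.

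All these analyses are descriptive, so no error rate or sample size is affected. This is an inexpensive improvement to a planned safety table.

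**What to change.** In SAP 7.2.2.5:

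1. Beside each interval's IAR rate, show the share of infusions in that interval given with pre-infusion medication and, where recorded, with a changed infusion rate. Protocol 11.5.1 already requires changes in premedication and rate for safety or tolerability to be documented. On the 2-week schedule no infusion is due on days 4 to 7, so no share can be shown there.
2. As a descriptive supplement, show the table by pre-infusion medication status at the ATB200-07 baseline, using the split in SAP 5.2.2. Note the small cells and that management may still change within each group.
3. Word any trend as holding under protocol IAR management. Do not conclude from this table, or from the baseline-premedicated group alone, that IARs disappear.

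The cost is SAP wording, added columns and one extra split of a planned table, from data the plan already lists or requires to be documented. The drawback is small cells. No clinical rule changes.

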**Table 9: Guidelines for Management of Early Infusion-associated Reactions**

Severity	Symptoms (such as, but not restricted to)	Management Guidelines
Mild reaction	Flushing Nausea Mild headache Tachycardia (pulse < 100 bpm) Abdominal pain	
REDUCE INFUSION RATE BY 50%
 
Contact investigator.
 
Give oral antihistamine/acetaminophen and/or IV antihistamine.
 
Prepare emergency equipment for any subsequent study drug escalation.
 
Subject must be observed at site or medical facility for 2 to 4 hours after resolution of the symptoms.
 
Record all details of times, concomitant medications and nondrug therapies, and infusion rates.
 
Record all details. Report AE, if applicable.
 
IF SYMPTOMS PERSIST:
 
STOP THE INFUSION
 
After 30 minutes, if subject has improved, increase to previous infusion rate on direction of investigator/designee.
 
If subject has not improved after 60 minutes, consult with investigator as to whether additional medications should be administered.
 
If subject reacts for second time after return to the prior infusion rate, reduce rate by 50% and contact investigator/designee.
 
IF IN DOUBT, STOP INFUSION

Moderate reaction	Localized itchiness, and/or raised Urticarial rash (hives) Severe headache Fever or shivering Tachycardia (pulse > 100 bpm) Tachypnea Flushing Nausea Irritability Headache Vomiting Diarrhea Abdominal cramps Myalgia	
** STOP INFUSION **
 
Immediately contact investigator.
 
Administer high-flow oxygen if respiratory symptoms/distress.
 
Give IM or IV antihistamines (eg, promethazine 25 to 50 mg).
 
Give IV fluid bolus, if warranted.
 
Give IV steroids (hydrocortisone 100 mg) on direction of investigator/designee.
 
Continue management as directed by the investigator/designee.
 
If deemed appropriate by investigator/designee, resume study drug infusion at reduced rate and prepare emergency equipment.
 
If deemed appropriate by investigator/designee, infusion can be suspended and reinitiated 48 hours later with premedications and at the infusion rate that was last tolerated.
 
Observe subject for a minimum of 6 hours after resolution of the event.
 
Record all details. Report AE, if applicable.

**Table 9: Guidelines for Management of Early Infusion-associated Reactions (Continued)**

Severity	Symptoms (such as, but not restricted to)	Management Guidelines
Severe reaction, anaphylaxis, or anaphylactoid reactions	Chest pain Generalized urticarial/angioedema Symptomatic hypotension (subject feeling faint, paleness) Hoarseness of voice/laryngeal edema Bronchospasm	
** STOP INFUSION **
 
Activate emergency response and immediately contact investigator.
 
For chest pain and symptomatic hypotension, initiate emergency procedures.
 
Administer high-flow oxygen or intubate and mechanically ventilate as appropriate.
 
Give IM adrenaline 300 mcg EpiPen into thigh (avoid buttock). If no response, repeat dose in 5 minutes. Prepare infusion of adrenaline 3 mg/50 mL NS (60 µg/mL), if needed.
 
Give IV fluids 10- to 20-mL/kg fluid bolus on direction of investigator/designee.
 
Give IV antihistamines (promethazine 25 to 50 mg in 10 mL WFI over 2 to 3 minutes).
 
Give IV steroids (hydrocortisone 100- to 500-mg bolus IV injection; dilute in 10 mL NS for doses between 100 and 500 mg) and infuse over 2 minutes.
 
Give nebulized beta-2 agonists with high-flow oxygen on direction of investigator/designee.
 
Administer other treatments and/or transfer patient to hospital/ICU as recommended by investigator/designee.
 
Observe subject for a minimum of 24 hours after resolution of the event.
 
If deemed appropriate by investigator/designee, study drug infusion can be re-initiated 7 to 14 days with premedications and at the 4-hour duration.
 
Record all details. Report AE, if applicable.

Abbreviations: AE = adverse event; GAA = human acid  $\alpha$ -glucosidase; ICU = intensive care unit; IgE = immunoglobulin E; IM = intramuscular; IV = intravenous; NS = normal saline; WFI = water for injection  
Source: [Vogel 2010](#); [Sampson, Muñoz-Furlong et al. 2006](#)

### 13.1.4. Relationship to Study Drug

The investigator or a qualified sub-investigator will review each event and assess its relationship to ERT based on available information according to the following guidelines:

- **Definite:** A reaction that follows a distinct temporal relationship from administration of the study drug, that follows a known reaction to the agent or chemical group of the study drug, and that cannot be explained by the subject's clinical state or other factors. By definition, IARs (immediate or late type) are considered definite (see Section 13.1.3).

- **Probable:** A reaction that follows a reasonable temporal sequence from administration of the study drug, that follows a known or expected response pattern to the suspected study drug, and that could not be reasonably explained by the known characteristics of that subject/subject's clinical state.
- **Possible:** A reaction that follows a reasonable temporal sequence from administration of the study drug and that follows a known or expected response pattern to the suspected study drug, but that could readily have been produced by a number of other factors.
- **Unlikely:** A reaction that does not follow a reasonable temporal sequence from administration of the study drug. However, causality from the study drug cannot be ruled out.
- **Unrelated:** A reaction for which sufficient data exist to indicate that the etiology is unrelated to the study drug.

For the purpose of reporting SAEs to regulatory authorities and IRBs/IECs/REBs, any AE assessed by the investigator as definitely, probably, or possibly related to study drug will be considered "related" to study drug (ie, associated with the use of the study drug). Any AE assessed as unlikely or unrelated will be considered "not related" to study drug (ie, not associated with the use of study drug).

### **13.1.5. Assessment of Severity**

The following definitions for rating severity will be used:

- **Mild:** Awareness of sign, symptom, or event, but the AE is easily tolerated and does not interfere with daily activity.
- **Moderate:** Discomfort enough to cause interference with usual activity and may warrant intervention, but the subject is still able to function.
- **Severe:** Incapacitating with inability to do usual activities or significantly affects clinical status and requires medical intervention.

When the determination of AE severity rests on medical judgment, the determination of severity must be made with the appropriate involvement of the investigator or a qualified sub-investigator.

